10.5. Reporting of Product Complaints

In geographies where devices are market-released, product complaint reporting is applicable. This includes when an AE is related to a market-released device during the study. The reporting of product complaints is not part of the clinical study and should be done in addition to the Adverse Event and Device Deficiency reporting requirements. Refer to local regulations for reporting requirements.

Product Complaint: Any written, electronic or oral communication that alleges deficiencies related to the identity, quality, durability, reliability, safety, effectiveness or performance of a medical device that has been placed on the market.

It is the responsibility of the Investigator to report all product complaint(s) associated with a medical device distributed by Medtronic, regardless whether they are related to intended use, misuse or abuse of the product. Reporting must be done immediately and via the regular channels for market-released products.

Medtronic will notify the regulatory authorities (e.g. FDA) as applicable for the following incidents immediately upon learning of them:

- Any malfunction or deterioration in the characteristics and/or performance of a device, as well as any inadequacy in the labeling or instructions for use which led or might have led to the death or serious deterioration in the state of health of a patient, user, or other person.
- Any technical or medical reason resulting in withdrawal of a device from the market by the manufacturer.
- A serious deterioration in the state of health includes:
 - Life-threatening illness or injury
 - Permanent impairment of a body function or permanent damage to a body structure
 - A condition necessitating medical or surgical intervention to prevent permanent impairment of a body function or permanent damage to a body structure

11. Data Review Committees

11.1. Data Monitoring Committee (DMC)

Study Oversight

Ongoing oversight for this study will be provided by an independent Data Monitoring Committee.

Who will be involved

The DMC will have one statistician with experience in the evaluation of clinical trials and at least two physicians that are not participating Investigators for the study. A chairperson from among those members will be identified.

Responsibility of the DMC

The DMC will be responsible for assessing the accumulating data on safety of the therapy during the study. The DMC will be responsible for safeguarding the interests of study subjects, assessing the safety of the PFA system during the study, and for monitoring the overall conduct of the clinical study. To enhance the integrity of the study, the DMC may also formulate recommendations related to the selection, recruitment, and retention of subjects, their management, improvement of adherence to protocol-specified regimens and procedures for data management and quality control.

Recommendations

The DMC will be advisory to the sponsor. The DMC may provide recommendations for early termination of the study. Review and consensus by the entire committee is required to recommend that the study should be stopped. The DMC may also make recommendations related to the selection, management and retention of subjects, improvement of adherence to protocol-specified regimens, and procedures for data management and quality control.

DMC Meetings

All DMC meetings may be conducted either in person or by teleconference. There will be an initial meeting prior to the start of the Pivotal Phase of the study. Additionally, the DMC will meet approximately every 6 months to review study data. The first meeting must be within 6 months of the first enrollment in the Pivotal Phase of the study. Reports will consist of data on study conduct and aggregate adverse events review. Once the study follow-up is completed, the DMC will be disbanded, with no need to review final results of the study.

11.2. Clinical Events Committee (CEC)

An independent Clinical Events Committee (CEC) will review and adjudicate, at a minimum, all procedure- and system-related adverse events, as well as all adverse events resulting in death.

The CEC will consist of a minimum of three (3) non-Medtronic employed physicians that are not participating Investigators for the study, including a CEC chairperson.

Medtronic personnel may facilitate and participate in a CEC meeting but will be non-voting members.

For adverse events and deaths reviewed by the CEC, Medtronic will provide the CEC with the Investigator's description and classification. The CEC is responsible for reviewing the Investigator's assessment and supportive documentation (when available), reviewing applicable definitions, and determining final classifications for all adjudication parameters. Additionally, the CEC will provide an adjudication of the death classification for all reported deaths including primary cause of death and death classification.

If the CEC disagrees with the Investigator's classification of the event, the difference will be provided to the Investigator. If the Investigator agrees with the CEC's adjudication, the eCRF documenting the event will be updated accordingly.

If the Investigator does not agree with the CEC's adjudication classification, both determinations will be provided within the final report; however, the CEC's adjudication will be used for data analysis. The disagreement will also be included in reporting to IRB/REB/MECs and regulatory authorities, if required.

12. Statistical Design and Methods

This section includes a description of the statistical methods and analyses to be included in reports that include analysis of endpoints. Any change to the data analysis methods described in the CIP will require an amendment to the CIP only if it changes a principal feature of the CIP. Any other change to the data analysis methods described in the CIP, and the justification for making the change, will be described in the clinical study report.

[figure not shown]
Standard baseline and relevant medical history will be collected on the CRFs for all enrolled subjects. Baseline variables to be summarized include, but are not limited to: age, sex, race (if allowed by local law), and physical exam findings.

Additional exploratory analyses of the data may be conducted as deemed appropriate.

Each arm (paroxysmal AF and persistent AF) of the Pivotal Phase of this study contains the following cohorts, with each enrolled subject belonging to one-and-only-one of the cohorts:

- Non-treated Cohort – Subjects enrolled in the study who exit prior to having the PFA system multielectrode catheter inserted into vasculature.
- Roll-in Cohort – roll-in subjects are defined in Section 7.2.1.
- Primary Analysis Cohort – Treated (those who have the PFA system multielectrode catheter inserted into vasculature) subjects who are not part of the Roll-in Cohort.

There is no intention to pool data from the Pilot Phase and the 3 Pivotal Phase cohorts. All will be analyzed separately.

12.1. Pilot Phase

12.1.1. Pilot Phase Safety Objective

Assess the incidence of PFA system-related and PFA procedure-related serious adverse events (SAEs) within 30 days post-ablation.

Endpoint Definition

Table 13 displays the PFA system-related and PFA procedure-related serious adverse events (SAEs) that will be considered a Pilot Phase safety event against the Pilot Phase safety endpoint.

Table 13: Analysis of Serious Adverse Events for Pilot Phase Subjects

Serious Adverse Event	Method of Analysis
pulmonary vein stenosis (>70% diameter reduction);	Review of symptoms post-procedure and at 30-day visit
phrenic nerve injury/diaphragmatic paralysis (ongoing at 30 days post-ablation);	
atrioesophageal fistula;	
cardiac tamponade/perforation;	
cerebrovascular accident;	Review of symptoms post-procedure and at 30-day visit; Confirmed by formal neurology assessment if required due to NIHSS assessments
major bleeding requiring transfusion;	Review of symptoms post-procedure and at 30-day visit
myocardial infarction;	
pericarditis requiring intervention;	
transient ischemic attack;	
vagal nerve injury resulting in esophageal dysmotility or gastroparesis;	
vascular access complications requiring intervention;	
death;	
any PFA system-related or PFA procedure-related cardiovascular and/or pulmonary adverse event that prolongs or requires hospitalization for more than 48 hours (excluding recurrent AF/AFL/AT)	

Analysis Methods

The percentage of procedures with a PFA system-related or PFA procedure-related SAE will be calculated as the number of procedures with at least one SAE meeting the endpoint definition divided by the number of PFA system ablation procedures. Each procedure will count, so subjects with repeat PFA system ablations will contribute more than once to the denominator. Exact methods will be used to construct a 95% confidence interval for the percentage of procedures with an SAE meeting the endpoint definition.

Determination of Subjects/Data for Analysis

All procedures in Pilot Phase subjects where the PFA system multielectrode catheter is inserted into vasculature will be included.

12.1.2. Pilot Phase Effectiveness Objective

Assess the acute procedural success of PVI ablation with the PFA system.

Endpoint Definition

Acute procedural failure is defined as:

- a. Inability to isolate all accessible targeted pulmonary veins (assessed for entrance block and, where assessable, exit block) during the index ablation procedure.
- b. Ablation using a non-study device to isolate any pulmonary vein.

Acute procedural success is the opposite of acute procedural failure.

Analysis Methods

The percentage of procedures with acute procedural success will be calculated as the number of procedures meeting the endpoint definition of acute procedural success divided by the number of PFA system ablation procedures. Each procedure will count, so subjects with repeat PFA system ablations will contribute more than once to the denominator. Exact methods will be used to construct a 95% confidence interval for the percentage of procedures with acute procedural success.

Additionally, acute success at the pulmonary vein level will be calculated. Each accessible targeted pulmonary vein will be classified as acute success or not. The percentage of total pulmonary veins attempted with the PFA system will be calculated. Exact methods will be used to construct a 95% confidence interval.

Determination of Subjects/Data for Analysis

All procedures in Pilot Phase subjects where the PFA system multielectrode catheter is inserted into vasculature will be included.

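### Pilot acute success: failure to isolate is defined only for the index procedure, but the percentage counts repeats, so a repeat that fails to isolate can score as a success

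*Combined protocol and SAP*

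**What the plan says.** Section 12.1.2 (Pilot Phase Effectiveness Objective) gives two ways to fail acutely. Criterion (a) is "Inability to isolate all accessible targeted pulmonary veins (assessed for entrance block and, where assessable, exit block) during the index ablation procedure". Criterion (b) is "Ablation using a non-study device to isolate any pulmonary vein" and is not tied to the index procedure. The complement rule follows: "Acute procedural success is the opposite of acute procedural failure".

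The analysis then works per procedure. The percentage is the "number of procedures meeting the endpoint definition of acute procedural success divided by the number of PFA system ablation procedures", and "Each procedure will count, so subjects with repeat PFA system ablations will contribute more than once to the denominator". On the interval: "Exact methods will be used to construct a 95% confidence interval for the percentage of procedures with acute procedural success". On the analysis set: "All procedures in Pilot Phase subjects where the PFA system multielectrode catheter is inserted into vasculature will be included".

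Repeats are foreseen. Section 8.7 allows repeat PVI with PFA inside the 90-day blanking period and requires any repeat with the system to follow the steps of Section 8.4. The synopsis also confines criterion (a) to the index procedure, so the restriction is not a slip in one sentence.

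**The concern.** The failure definition and the denominator use different units. Criterion (a) can be met only at the index ablation, whereas the denominator takes in every procedure. Because success is whatever is not failure, a repeat cannot fail on isolation. It can fail only on (b), and otherwise adds one to both numerator and denominator.

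What is at stake is the acute-success figure from the first 20 people treated with a first-in-human system. Readers will take it as the share of procedures in which all accessible targeted veins were isolated. For repeats, the rule as written does not measure that.

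**Working it through.** **No plan figure to reproduce.** The documents state no expected rate, precision or power for this endpoint. The size of the effect therefore has to be illustrated.

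**Inputs**
- Pilot subjects: n = 20 (synopsis; Section 5).
- Index failures f: assumed 0 to 2.
- Repeat PFA procedures r: assumed 0 to 4. The documents give no expected number.
- Interval: Clopper-Pearson 95%. The lower limit is the 2.5% quantile of Beta(x, N−x+1) and the upper limit is the 97.5% quantile of Beta(x+1, N−x). Applied to five rows of Table 14, with event counts taken as rate × n and rounded, it returns the printed exact intervals to within 0.1 point.

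**Step 1: classify a repeat under the text.**

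| Repeat procedure | Criterion (a) | Criterion (b) | Scored as |
|---|---|---|---|
| All veins isolated, PFA only | cannot apply | not met | success |
| A vein not isolated, no other device used | cannot apply | not met | success |
| Non-study device used to isolate a vein | cannot apply | met | failure |

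The second row is the defect. It can arise because Section 8.4.4(j) permits, but does not require, another catheter when isolation fails.

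**Step 2: size under the literal rule.** With no non-study device used in repeats, the rule gives (20 − f + r)/(20 + r). Index-only gives (20 − f)/20.

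| f | Index-only | r = 2 | r = 3 | r = 4 |
|---|---|---|---|---|
| 0 | 20/20 = 100% (lower 83.2%) | 22/22 (84.6%) | 23/23 (85.2%) | 24/24 (85.8%) |
| 1 | 19/20 = 95.0% (75.1%) | 21/22 = 95.5% (77.2%) | 22/23 = 95.7% (78.1%) | 23/24 = 95.8% (78.9%) |
| 2 | 18/20 = 90.0% (68.3%) | 20/22 = 90.9% (70.8%) | 21/23 = 91.3% (72.0%) | 22/24 = 91.7% (73.0%) |

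The largest shift in this grid is 91.7 − 90.0 = 1.7 points on the estimate and 73.0 − 68.3 = 4.7 points on the lower limit.

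**Step 3: the misclassification alone.** Take f = 1 and r = 3, and suppose one repeat fails to isolate a vein with no other device used. The literal rule still reports 22/23 = 95.7% (lower 78.1%). Judging each procedure on its own result gives 21/23 = 91.3% (lower 72.0%).

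**Step 4: expected size.** With index success probability p and q repeats per subject, all scored as successes, the expected rate is about (p + q)/(1 + q). Taking p = 0.98 from the 2% acute-failure assumption in the Pivotal simulation (Section 12.2.3), and q = 0.05 to 0.20, the rate is (0.98 + 0.05)/1.05 = 98.1% to (0.98 + 0.20)/1.20 = 98.3%, against 98.0% on index procedures.

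**The case against.** The strongest reply is that the sponsor means to judge every repeat on its own isolation result. Section 8.7 sends repeats through the Section 8.4 steps, Section 8.4.4(h) requires each vein to be verified, and Section 8.4.6 records demonstrated block. The data exist, and the index wording may have been carried over from the similar Pivotal definition. That is plausible, but Section 12.1.2 does not say it and its criterion (a) contradicts it. A reader could also go the other way and deny repeats any index success, which with f = 1 and r = 3 gives 19/23 = 82.6%. The upward direction therefore belongs to the literal reading. What stands of the objection is that the effect is small and the remedy is mainly wording.

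Three stronger readings are tempting, and the documents do not support them.

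- **Pilot safety rate biased downward.** Section 12.1.1 uses the same denominator but has no index-only wording, and it counts any procedure with a qualifying event, repeats included. Numerator and denominator match. With one index event and three repeats the result could be 1/23 = 4.3% or, with one repeat-related event, 2/23 = 8.7%, against 1/20 = 5.0%. No direction is fixed.
- **Exact intervals shown to be too narrow.** Two procedures in one subject need not be independent, but Clopper-Pearson is conservative at this size. For 17 subjects with one procedure and 3 with two, coverage stays above 95% at an intraclass correlation of 0.2 for rates up to 20%. It falls only to about 93% at a correlation of 1.
- **Difference from the Pivotal Phase as an error.** Section 12.2.2 uses index procedures only for safety, but the phases are separate data sets with no intention to pool (Sections 3.2 and 12), so they may use different units.

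**Conclusion.** The inconsistency holds for the Pilot effectiveness endpoint only. As written, Section 12.1.2 scores a repeat that fails to isolate a vein as a success unless a non-study device was used, and this can inflate the reported rate. With 0 to 4 repeats and 0 to 2 index failures, both assumed, the shift is under 2 points on the estimate and under 5 on the lower limit. It vanishes if no repeats occur.

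The visible text attaches no hypothesis or performance goal to this endpoint, and Pilot subjects are excluded from the Pivotal primary and secondary endpoint analyses, so no power or type I error is affected. This is a minor correction worth making because it costs almost nothing.

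**What to change.** In Section 12.1.2, compute the acute-success percentage and its exact 95% interval on index procedures, one per subject, with a denominator of 20. Report repeat PFA procedures separately, each classified on its own isolation result and on non-study device use.

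If the per-procedure denominator is kept, the minimum change is to replace "during the index ablation procedure" in criterion (a) with *during that procedure*, so that numerator and denominator share a unit.

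Leave the Section 12.1.1 safety percentage as it is. Moving it to index procedures would take repeat-related events out of the headline figure, a trade-off this point does not settle.

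The cost is a wording change with no new data or subjects. The index-only interval is slightly wider: in the worked case its lower limit is 75.1% rather than 78.1%.

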6.1. General

Device information is described below and provided in Table 5 and Table 6. Investigator’s Brochure (IB) and Instructions For Use (IFU) of the PFA system will be provided to investigational sites for use in the clinical study.

Any changes made to these devices during the investigation will be subject to IDE Change or Modification Reporting Requirements per 21 CFR Part 812, as applicable (see Section 13.1).

Table 5: PFA System Components

Component	Model Number	Geography Status at Study Start	[REDACTED]
PFA Generator	M970163A001	Investigational in all geographies	[REDACTED]
Catheter Electrode Distribution System (CEDs)	M970165A001	Investigational in all geographies	[REDACTED]
Remote Control	M970127A001	Investigational in all geographies	[REDACTED]
Cable, Generator to Remote Control	M970169A001	Investigational in all geographies	[REDACTED]
Cable, Generator to CEDs	M970168A001	Investigational in all geographies	[REDACTED]

[figure not shown]

Table 6: PFA System Accessories

Accessory	Model Number	Geography Status at Study Start*	
Cable, CEDS to EP Recording System (EGM)	990027	Commercially available in Europe, Canada, and Australia. Investigational in other geographies.	
Cable, Sterile, Catheter to CEDS	990004	Commercially available in Europe, Canada, and Australia. Investigational in other geographies.	
	990078	Commercially available in Europe, Canada, and Australia. Investigational in other geographies.	
Cardiac Trigger Monitor and Cable	7700	Commercially available in Europe, Canada, Australia, and US. Investigational in Japan.	
Power Cord	1038N – North America; Japan 1038K – Australia 1038E – EU	Commercially available in all geographies	
Uninterruptable Power Supply (UPS)	SMART1200XLHG (120V) SMX1200XLHG (230V)	Commercially available in all geographies	
Power Cord – C14M-C13F	P004-006-ABL	Commercially available in all geographies	

*All PFA system accessories will be considered investigational when used with PFA system

It is anticipated that at least 415 [REDACTED] catheters and 415 Sterile, Catheter to CEDS, Cables will be used to ensure the study sample size is met. It is anticipated that at least one each of the remaining PFA system components and accessories will be used per site in the study.

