6.1.1. System Description

The Medtronic Pulsed Field Ablation (PFA) system applies bipolar, biphasic pulsed electric fields through a circular multi-electrode array catheter to perform cardiac tissue ablation through irreversible electroporation. The system is intended to be used for the treatment of atrial fibrillation in humans by isolation of the major cardiac veins.

Each PFA therapeutic delivery consists of a series of electric pulses delivered as a pulse train containing individual brief biphasic pulses. During each pulse, current flows in a bipolar manner between individual electrodes on the multi-electrode catheter array which radiates an electric field that surrounds the array. Cardiac tissue within the electric field undergoes cellular hyper-permeabilization, which irreversibly disrupts the integrity of the cellular membrane leading to cell death in the targeted tissue site. This mechanism of cell death is known as irreversible electroporation (IRE). The ablated myocardium then undergoes replacement fibrosis over a period of days to weeks creating a fibrotic lesion.

[REDACTED]
[REDACTED]
[REDACTED] catheters are sterile, single-use only intravascular devices designed for short-term use (< 24 hours) within the human vasculature and heart. [REDACTED] makes contact with the central circulatory system (blood contact). [REDACTED] is also intended for cardiac EP mapping of pulmonary vein potentials, delivery of diagnostic pacing stimuli and verifying electrical isolation of the pulmonary veins post-treatment. The PFA system is utilizing this catheter as a platform to deliver pulsed electric fields to cardiac tissue.

The PFA system is for use by physicians in a clinical setting (e.g. a fully equipped electrophysiology laboratory) and has been developed for use under a clinical protocol and not for general commercial use.

[REDACTED]

[Redacted content]

[Redacted content]

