8.3. Enrollment, Baseline, and Pre-ablation

When a patient and the Principal Investigator or authorized designee, as required, have signed and dated the IC Form, the patient is considered a subject enrolled in the study. The date the subject signed the IC Form and Authorization to Use and Disclose Personal Health Information/Research Authorization/other privacy language as required by law must be documented in the subject's medical records.

The baseline visit can be a standalone visit or can be performed on the same day but prior to the PFA system ablation procedure. The following evaluations will be performed after consent, unless previously performed as part of routine clinical evaluations within the specified windows:

Within 6 months prior to consent date:

- Trans-thoracic echocardiogram (TTE) for the collection of left atrial size, left ventricular ejection fraction, and mitral valve impairment. A repeat TTE procedure for the purpose of the study after the consent date is not required if a TTE was performed within 6 months of the consent date and all data are available.
- Pilot Phase subjects only: cardiac Magnetic Resonance Imaging (MRI) or Computerized Tomography Scanning (CT scan) of the four PVs or their anomalous equivalent.

Within 30 days prior to consent date:

- 12-lead ECG
- Physical examination
- CHA₂DS₂-VASc Score
- Demographics
- Medical history

After consent date but prior to procedure:

Note: The time between the consent date and the procedure should not exceed 30 days. If 30 days are exceeded, the subject must be re-evaluated against inclusion and exclusion criteria to ensure they still qualify for the study.

- Final assessment of all factors specified for evaluation under Inclusion Criteria and Exclusion Criteria (Section 7)
 - Note: After required study testing, if a subject no longer meets the inclusion criteria or now meets exclusion criteria, the subject will be exited from the study.
- Pregnancy screen (female subjects of child bearing potential only)
 - Note: For this study, a woman of childbearing potential is defined as a premenopausal female capable of becoming pregnant

- Review of AF symptoms
- Review of medications to treat atrial arrhythmias and anticoagulation medications
 - Amiodarone use must be discontinued at least 14 days prior to the ablation procedure and not restarted after the ablation procedure.
- EQ-5D (5L version) and AFEQT Questionnaires
- INR assessment

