- The number of Primary Analysis Cohort subjects enrolled per month will average 5 (1st month), 7 (2nd month), 11, 24, 35, 43, 51, 56, 60, 60, 60...
- Daily enrollments follow a Poisson distribution with an average of $x/30$, where x is the average number of enrollments in that month. This allows multiple ablation procedures in a day.
- 50% of enrollments are persistent AF subjects, and the other 50% are paroxysmal AF subjects
- 12-month effectiveness rate = 68% (A weighted average 12-month effectiveness was calculated at the bottom of the Table 15, resulting in an average effectiveness rate of 73.2%. Only three of the studies utilized weekly TTM (similar to the weekly patient activated ambulatory monitoring requirement), so due to the additional arrhythmia monitoring and a more stringent endpoint definition in PULSED AF, the 12-month paroxysmal AF effectiveness point estimate for this study has been set to 68%.)
- 6-month effectiveness rate = 79% (based on past studies (Table 15), the 6-month rate is approximately 11% higher than 12-month rate)
- 2% of patients will have an acute failure and these will occur on the first day post-ablation procedure
- Chronic failures (AF recurrence) occur either in the 3-6 month period or in the 6-12 month period, based on the assumed 68% and 79% numbers above.
- A patient with a chronic failure in the 3-6 month period has an equal chance of that failure occurring any day between 91 and 182 days post-ablation procedure
- A patient with a chronic failure in the 6-12 month period has an equal chance of that failure occurring any day between 184 and 364 days post-ablation procedure
- 5% attrition from ablation (drop out) procedure to 12 months
- Attrition occurs uniformly from 1-364 days post-ablation procedure
- [REDACTED]

Given the above assumptions, for the Paroxysmal AF arm of the study, a sample size of 165 Primary Analysis Cohort subjects is required.

To ensure proper characteristics of the study, especially alpha-level, the simulation program was rerun with all of the above assumptions (including the sample size of 165 subjects) the same, except that the assumed 12-month effectiveness rate was set to the null hypothesis rate of 55% (and 6-month effectiveness rate to 66%). [REDACTED]

[REDACTED] This meets the goal of having overall alpha being less than 2.5%.

Assumptions (Persistent Arm)

- The overall alpha will be 0.025, [REDACTED]
- Power=90%

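### The Pilot vein-level acute success interval treats about 80 veins from 20 subjects as independent, so its 95% level is not assured; the practical effect is small

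*Combined protocol and SAP*

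**What the plan says.** Section 12.1.2 makes the percentage of procedures with acute success the main Pilot effectiveness result and puts an exact 95% interval on it. It then adds a vein-level result. Each accessible targeted vein is classed as success or not, "The percentage of total pulmonary veins attempted with the PFA system will be calculated", and "Exact methods will be used to construct a 95% confidence interval" for that percentage as well. No cluster term, subject-level resampling or label is given. The analysis set is procedures, not subjects: "All procedures in Pilot Phase subjects where the PFA system multielectrode catheter is inserted into vasculature will be included".

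The other relevant facts are scattered:
- The Pilot Phase treats 20 subjects (Section 5).
- Section 8.3 refers to imaging "of the four PVs or their anomalous equivalent".
- Section 12.2.3 assumes for the Pivotal arms that "2% of patients will have an acute failure and these will occur on the first day post-ablation procedure".
- The introduction to Section 12 states: "There is no intention to pool data from the Pilot Phase and the 3 Pivotal Phase cohorts".

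Section 12.1.2 does not say which exact method is meant. The Table 14 footnote and the safety sample size in Section 12.2.2 both specify binomial exact methods.

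**The concern.** A binomial exact interval has its nominal level only if the units counted are independent. Veins in one subject share an anatomy, an operator and a session, so positive correlation is plausible. If it exists, 80 veins carry less information than 80 independent trials, and an interval computed on 80 is narrower than one that treats the subject as the cluster. The plan also leaves open whether a vein re-attempted at a repeat procedure is counted again.

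What is at stake is the accuracy of one descriptive interval in a first-in-human report. No hypothesis, performance goal or decision rule uses it.

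**Working it through.** The plan states no vein count, interval or width for this analysis, so there is no figure to reproduce. As a check on the meaning of exact, the Clopper-Pearson method was applied to two Table 14 rows. It gives 7.3% to 13.7% for 38/374 and 1.7% to 14.6% for 4/67, as printed there.

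**Inputs.** From the documents: 20 subjects, four veins each (20 x 4 = 80, derived), and 2% patient-level acute failure (a Pivotal figure). Assumed: within-subject correlation r from 0.1 to 0.5, and all acute failures arising from non-isolation.

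**Pooled interval.** With 80/80 the lower limit is 0.025^(1/80) = 95.5%. With 79/80 the interval is 93.2% to 99.97%. The upper limits for 78/80 and 77/80 are 99.70% and 99.22%.

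**Model.** Successes per subject are beta-binomial with m = 4, a = p(1-r)/r and b = (1-p)(1-r)/r. Vein success p is matched to the plan by requiring P(all four succeed) = 0.98. For r = 0.3, a + b = 2.333 and p = 0.99247, so a = 2.3158. The product (a/2.333)((a+1)/3.333)((a+2)/4.333)((a+3)/5.333) is then 0.980. Convolving 20 such subjects gives the exact distribution of the pooled count, without simulation.

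| r | matched vein success | coverage of pooled 95% interval | upper-limit misses |
|---|---|---|---|
| 0.1 | 99.42% | 97.4% | 2.6% |
| 0.2 | 99.34% | 95.3% | 4.7% |
| 0.3 | 99.25% | 92.9% | 7.1% |
| 0.4 | 99.15% | 95.4% | 4.6% |
| 0.5 | 99.03% | 93.1% | 6.9% |

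Lower-limit misses are zero throughout, because the highest possible lower limit (95.5%, at 80/80) is below every matched p.

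**Finer grid.** In steps of 0.01 from 0.10 to 0.50, coverage is at least 95% at 21 of 41 points: 0.10 to 0.21 and 0.33 to 0.41. The minimum is 92.4% at 0.32. At 0.33 it jumps to 96.7%, because the matched p drops below 99.22% and a count of 77/80 then covers it. Much of the pattern is therefore discreteness. With patient failure from 1% to 5%, the range over the same correlations is 90.2% to 98.8%, still with no lower-limit misses.

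**Lower success.** At p = 95%, coverage is 93.6%, 90.5%, 87.1% and 79.2% for r = 0.1, 0.2, 0.3 and 0.5. Lower-limit misses are then 6.5% at r = 0.3 and 12.0% at r = 0.5. These settings imply patient failure of 12.7% at r = 0.3 and 10.1% at r = 0.5, at least five times the plan's 2%.

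**Subject-level bound.** For 20/20 subjects the lower limit is 0.025^(1/20) = 83.2%. The all-veins success rate cannot exceed the vein success rate, so this is a conservative lower bound for the latter. Under the 2% assumption, P(80/80) = 0.98^20 = 0.67 whatever r is, so this is the likeliest result.

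**Repeat procedures.** One repeat with four successes moves the perfect-result lower limit from 95.5% to 0.025^(1/84) = 95.7%. At procedure level, failure limb (a) is tied to the index procedure, so a repeat can fail only through limb (b), use of a non-study device, yet it adds to the denominator: 19/20 = 95.0% becomes 20/21 = 95.2%.

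**The case against.** The strongest reply is that the exact method is itself conservative and absorbs modest correlation: at the plan's 2% figure, coverage is nominal or better up to about r = 0.21 and again from 0.33 to 0.41. That stands. It also stands that the correlation is not in the documents, so both the effect and its smallness depend on the range chosen; at 2% failure and r = 0.7, coverage would be 86.4%. The procedure-level interval reported alongside already shows subject-level precision. Section 5.3 promises a statistical analysis plan that may settle the method.

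Two stronger readings are tempting, and neither is supported:
- A reader might infer that the interval overstates device success. At the plan's rates every miss is an upper limit that is too low, which errs the other way. Lower-limit misses appear only in the low-success setting.
- A reader might take the supply figures as proof that veins within a subject are correlated: the "catheters are sterile, single-use only intravascular devices designed for short-term use", and 415 = 20 + 80 + 315 treated subjects. But the text reads "It is anticipated that at least 415 [REDACTED] catheters and 415 Sterile, Catheter to CEDS, Cables will be used". That is a floor on supply, and sharing a catheter does not establish correlated outcomes.

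What remains is that the text specifies an inferential interval without stating or addressing the independence it needs.

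**Conclusion.** The point holds as a minor one. The pooled vein-level interval has no assured 95% level when veins within a subject are correlated. At the plan's expected success rate the departure is small and not uniform: about 92% to 97% coverage for r between 0.1 and 0.5. It becomes material, 87% to 79%, at r of 0.3 to 0.5 if vein success is near 95%. This rests on reading exact as binomial exact, on four veins in each of 20 subjects, on a beta-binomial model, on correlations that are assumed, and on applying a Pivotal failure rate to the Pilot. The result is supplementary, so no study conclusion turns on it. The repeat-procedure denominator is a separate and still smaller matter.

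**What to change.** Amend the vein-level paragraph of Section 12.1.2, or specify the following in the statistical analysis plan:
- Count each vein once, at the index procedure.
- When failures are spread over enough subjects to estimate clustering, compute the interval with the subject as the cluster, for example an exact interval on the effective sample size or a subject-level bootstrap.
- When all or nearly all veins succeed, correlation cannot be estimated, and with no failures a bootstrap has no width. Report the pooled interval as not adjusted for veins within subject, and give the subject-level exact interval beside it as the conservative bound. This is preferable to printing bounds at assumed correlations.
- Separately, use one index procedure per subject as the procedure-level denominator and list repeat procedures on their own.

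The cost is a few sentences and a few lines of code on data already collected. The downside is a wider, somewhat conservative interval. With a known correlation of 0.1 to 0.5, the effective-sample-size version covers 98.5% to 99.4% at the rates matched to 2% patient failure.
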